### 3. **Abstract:**

**Background/Purpose:** Falls are a common and costly complication following stroke. While residual walking and balance deficits contribute substantially to long-term disability, of greater concern for this population is the incidence of falls. Between 40% and 70% of individuals fall within their first year post-stroke. Individuals who fall have increased incidence of serious adverse outcomes, including fractures, depression, and mortality. A primary goal of stroke rehabilitation is to improve mobility in the presence of motor, balance, and visual-spatial deficits. The conundrum all stakeholders must face is that increased mobility may increase risk for falls, whereas limiting walking and general mobility will lead to a multitude of deficits associated with inactivity, including recurrent stroke. Because of these serious consequences, there is an urgent need in the rehabilitation of Veterans with stroke to both identify those who are at fall risk and develop intervention strategies that will reduce fall incidence while increasing mobility. Backward walking has recently emerged as both a potential predictor of fall incidence as well as an intervention modality to prevent future falls. However, it has not yet been assessed under the rigors of a controlled trial. We will conduct a randomized controlled trial with three specific aims to examine 1) the effectiveness of Backward Walking Training (BWTraining) early poststroke in decreasing falls, 2) the timing of BWTraining delivery to increase Backward Walking speed (BWSpeed), and 3) the relationship between BWSpeed and prospective fall incidence.

**Subjects:** One-hundred twenty-eight individuals, 2 months post-stroke, will participate. Additional study criteria include: 1) ambulatory with gait speed < 0.8 m/s; 2) community-dwelling; 3) Berg Balance Scale < 42; 4) absence of other neurological conditions; 5) discharged from physical therapy services; 6) stable cardiac status; 7) absence of lower extremity orthopedic impairments or pain that limits gait ability.

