one of the nation's largest inpatient rehabilitation hospitals and stroke is their largest diagnostic category, with approximately 600 stroke admissions per year. Research studies within this entity are conducted under the auspices of their Clinical Research Center. Brooks Rehabilitation Clinical Research Center maintains an IRB-approved registry of individuals who have experienced a neurological injury, approximately 640 individuals with a stroke diagnosis who have signed HIPAA Authorization and can be contacted regarding research trial participation. Potential participants will be contacted via phone and a phone screen will be conducted. The phone screen script is provided in a separate document. If individuals pass the phone screen, they will be invited and scheduled for an in-person screen. Information obtained from the phone screen will only be shared with study personnel and will be stored in a locked cabinet in a locked room. b. Individuals who respond to an IRB-approved advertisement. They will undergo phone screen as above. c. Individuals who signed a Brooks Notice of Privacy Practices upon Brooks admission (which indicates their information may be used for research) will have their medical records reviewed by study personnel and if appropriate will be provided an IRB-approved study flier. If interested, they will have the opportunity to sign the Screening Informed Consent and complete the Screening Assessment while they are an inpatient. If they prefer to wait until they are discharged from inpatient rehabilitation, they will be contacted at six-weeks post-stroke to determine their continued interest and confirm eligibility. Women and members of diverse ethnic and racial groups will be actively recruited.

*Inclusion criteria:* 1) Diagnosis of unilateral stroke, 2)  $\geq 2$  months  $\leq 4$  months post-stroke, 3) Berg Balance Scale  $\leq 42$ , 4) Self-selected 10 meter gait speed  $< 0.8$  m/s, 5) Able to ambulate at least 10 feet with maximum 1 person assist, 6) Medically stable, 7) 18-95 years of age, 8) living in the community, 9) Unilateral lower extremity paresis confirmed by a score of  $< 32$  on the Fugl-Meyer Motor Assessment, 10) Physician approval for patient participation.

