*Exclusion criteria:* 1) Presence of neurological condition other than stroke, 2) Serious cardiac conditions (hospitalization for myocardial infarction or heart surgery within 3 months, history of congestive heart failure, documented serious and unstable cardiac arrhythmias, hypertrophic cardiomyopathy, severe aortic stenosis, angina or dyspnea at rest or during activities of daily living). Anyone meeting New York Heart Association criteria for Class 3 or Class 4 heart disease will be excluded, 3) Severe arthritis or orthopedic problems that limit passive ranges of motion of lower extremity (knee flexion contracture of  $-10^\circ$ , knee flexion ROM  $< 90^\circ$ , hip flexion contracture  $> 25^\circ$ , and ankle plantar flexion contracture  $> 15^\circ$ ), 4) Severe hypertension with systolic greater than 200 mmHg and diastolic greater than 110 mmHg at rest, that cannot be medically controlled into the resting range of 180/100 mmHg. 5) Pain upon ambulation, , 6) Unable to ambulate at least 150 feet prior to stroke, or experienced intermittent claudication while walking less than 200 meters, 7) Living in a skilled nursing facility, 8) History of serious chronic obstructive pulmonary disease or oxygen dependence, 9) Non-healing ulcers on the lower extremity, 10) Uncontrollable diabetes with recent weight loss, diabetic coma or frequent insulin reactions, 11) On renal dialysis or presence of end stage liver disease, 12) Pulmonary embolism within previous 6 months, 13) History of major head trauma, 14) History of sustained alcoholism or drug abuse in the last six months, 15) Current enrollment in a clinical trial to enhance stroke motor recovery, 16) Intracranial hemorrhage related to aneurysmal rupture or an arteriovenous malformation, 17) Injection of lower extremity muscle relaxant in the past 6 months

Inclusion and Exclusion criteria will initially be determined by medical record review. If following the medical record review a potential participant remains eligible, they will be scheduled for an in-person screen to determine if they meet the criteria listed below. Potential participants will sign the screening Informed Consent Form and then the following screening assessments will be administered:

1. Berg Balance Scale: This tool consists of 14 items that assesses static and dynamic standing balance, ability to sit, stand up and transfer.

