#### **7. Possible Discomforts and Risks:**

The risks undertaken in the walking therapy programs of the study are no greater than those in everyday physical therapy clinics where persons who have had a stroke are challenged daily to exercise, train, practice and improve beyond their current abilities. Safety in therapy is mandatory. Research personnel will walk beside participants during all aspects of the exercise intervention and all aspects of the assessment that assess gait and balance. Participants may experience some fatigue while being tested or during the therapy sessions. Should they become tired, they will be allowed to rest. Participants may experience temporary muscle soreness as they increase the use of their trunk and limbs during the walking intervention. There is a risk of falling during walking activities, but guarding by research personnel will minimize the risk. Stroke patients, including those in this study, are at risk for another stroke, coronary heart disease related event and cardiac related death, regardless of intervention.

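### Exclusion item 4 joins its two blood-pressure limits with 'and', so read literally it does not exclude an uncontrolled patient who is over only one of them

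*Combined protocol and SAP*

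**What the plan says.** Section 6 (Research Plan), exclusion item 4, reads "Severe hypertension with systolic greater than 200 mmHg and diastolic greater than 110 mmHg at rest", followed by the qualifier "that cannot be medically controlled into the resting range of 180/100 mmHg". As written, three conditions must all hold: systolic above 200, diastolic above 110, and failure to reach 180/100 with treatment.

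The other entry conditions that could stop such a patient are general. The inclusion list in the same section requires the patient to be "Medically stable" (item 6) and requires "Physician approval for patient participation" (item 10). The Abstract adds "stable cardiac status". None of these gives a pressure. The five in-person screening assessments are the Berg scale, the 10-metre walk, the lower-extremity Fugl-Meyer, range of motion and the 3-metre backward walk. No blood-pressure measurement is listed among them.

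Elsewhere in the exclusion list, alternatives are usually joined by 'or'. Examples are item 8, "History of serious chronic obstructive pulmonary disease or oxygen dependence", and item 11, "On renal dialysis or presence of end stage liver disease".

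**The concern.** A severe-hypertension exclusion before exercise would normally apply when either component is too high. With 'and', a very high systolic pressure with a diastolic of 110 or less passes the item. So does a very high diastolic with a systolic of 200 or less.

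The patients are two to four months post-stroke and go on to 18 to 21 sessions of treadmill and overground stepping. Section 7 acknowledges the background hazard: "Stroke patients, including those in this study, are at risk for another stroke, coronary heart disease related event and cardiac related death". If the only numeric limit does not act on a patient over a single limit, the decision rests on unquantified judgement. Eligibility is first determined from medical records, and recruitment runs at two sites, so two screeners could reach opposite answers on the same recorded values. This is a participant-safety and consistency point. It does not bear on the primary comparison.

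**Working it through.** The plan has no figure of its own to reproduce here. The check is logical, followed by an illustrative calculation of size.

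**1. The rule under each wording.** Let S be resting systolic pressure, D resting diastolic pressure, and U the condition that pressure cannot be brought to 180/100.

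- As written: (S > 200 and D > 110) and U
- With 'or': (S > 200 or D > 110) and U

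For patients who meet U:

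| Resting pressure | S > 200 | D > 110 | Excluded as written | Excluded with 'or' |
|---|---|---|---|---|
| 230/105 | yes | no | no | yes |
| 190/120 | no | yes | no | yes |
| 210/115 | yes | yes | yes | yes |
| 190/105 | no | no | no | no |

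There are 2 × 2 × 2 = 8 combinations of the three conditions. The literal rule excludes 1 and the 'or' rule excludes 3. The two that change are uncontrolled systolic-only and uncontrolled diastolic-only. This counts cases and says nothing about how often each occurs.

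**2. Consistency with the control target.** 230/105 exceeds 180/100 on both components (230 > 180, 105 > 100), and so does 190/120 (190 > 180, 120 > 100). The literal trigger therefore passes patients whom the same sentence treats as outside the acceptable range.

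**3. How the list uses connectives.** Eight of the 17 exclusion items (2, 3, 6, 8, 10, 11, 14 and 16) use 'or' where either condition is enough. Against that, the bracket in item 3 joins its range-of-motion limits with 'and' where any one is plainly meant. The usage is mixed, so item 4 can be read either way.

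**4. Illustrative size.** The documents give no blood-pressure distribution, so everything in this step is an assumption. S and D are taken as bivariate normal, with:

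- mean S 140, 150 or 160; SD 18 or 22
- mean D 80, 85 or 90; SD 10 or 14
- correlation 0.4, 0.6 or 0.8

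That makes 3 × 2 × 3 × 2 × 3 = 108 scenarios. For each,

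- P(either) = P(S > 200) + P(D > 110) − P(both)
- P(exactly one) = P(either) − P(both)

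One scenario in full, with means 150/85, SDs 22/14 and correlation 0.6:

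- P(S > 200) = P(Z > 50/22 = 2.27) = 0.0115
- P(D > 110) = P(Z > 25/14 = 1.79) = 0.0371
- P(both), from the bivariate normal = 0.0046
- P(either) = 0.0115 + 0.0371 − 0.0046 = 0.0440
- P(exactly one) = 0.0440 − 0.0046 = 0.0395 before rounding of the inputs, or 142 × 0.0395 = 5.6 people
- P(both)/P(either) = 10%

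Across all 108 scenarios:

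| Quantity | Minimum | Median | Maximum |
|---|---|---|---|
| Over both, as share of those over at least one | 0.3% | 5.5% | 30% |
| Over exactly one, per 142 | 0.2 | 3.5 | 13.0 |
| of which systolic-only, per 142 | 0.0006 | 0.4 | 4.8 |

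The median share of diastolic-only cases among those over exactly one limit is about 77%. All counts are before medical control, so the number who also meet U is smaller by an amount the documents do not let us estimate.

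**The case against.** The strongest reply is that nobody would apply the item literally. The closest parallel, the item 3 bracket, also lists several numeric limits with 'and' and clearly means any one of them. Most of the items that use 'or' join separate diagnoses or events, not two components of one measurement, so counting them is weak evidence. The 180/100 target points the same way, since a patient at 230/105 misses it on both components. A physician must approve every participant and staff must judge each one medically stable, so enrolling such a patient would take two further lapses.

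The size is also open to attack. The distributions are assumed, and most of the patients over one limit are diastolic-only, whereas the more striking example is systolic-only (median 0.4 per 142). The control condition could reduce the affected number to zero. Nor does the sentence in section 7 tie training to blood pressure. It describes a risk present whatever the intervention.

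Much of this stands. That 'or' was intended is the likelier reading, though the documents do not say so, and the practical gap is limited. None of it makes the written rule correct. A numeric criterion is there so that the decision does not rest on general judgement alone, and wording that can be read two ways in the only such criterion is itself a reason to amend it.

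**Conclusion.** The concern holds as a wording fault in an operative safety criterion. Followed literally, item 4 admits uncontrolled patients who exceed one limit but not the other, and no other passage supplies a blood-pressure figure that would stop them. This conclusion rests on the text alone.

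The size is uncertain and probably small. Across the assumed distributions, at least 70% of patients over any limit are over only one (100% − 30%), so the literal rule would miss most of the group it appears meant to catch, provided control fails about equally often in patients over one limit and over both. The absolute number is a handful per 142 at most before control, and fewer after it. The general entry conditions remain as a backstop. The 200/110 trigger and the 180/100 target are not in dispute. The change should be made, but nothing in the trial's statistical conclusions depends on it.

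**What to change.** In exclusion item 4, replace the 'and' between the systolic and diastolic limits with 'or'. Leave 200, 110, 180 and 100 as they are, and keep the control qualifier, so that the item excludes anyone over either limit whose pressure cannot be brought to target.

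The cost is a one-word amendment and possibly a few more screen failures. Sample size, visits and analysis are unaffected.

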
### **Identification of Fall Risk is Necessary to reduce Future Falls.**

Identification of individuals at risk for falling is an important aspect of post-stroke rehabilitation in order to implement pro-active measures both intrinsically (related to the individual) and extrinsically (associated with their environment). Clinical tests of walking speed and postural balance to predict fall risk after stroke have been reported previously. Gait speed has been reported to predict fall risk both in community-dwelling elderly and in individuals post-stroke. A recent, intriguing finding, worthy of further exploration is that backward, more so than forward walking identified, in a cohort of community-dwelling elderly, those that had fallen in the previous 6 months. Walking backward at a speed less than 0.6 m/s identified 100% of fallers and those who walked backward at a speed less than 0.4 m/s had a 3.2 times greater likelihood of being a faller than those who walked faster. In comparison, forward walking velocity at a cut off of 1.0 m/s only identified 83% of fallers. If BWSpeed is a more reliable predictor of falls than forward walking speed in the post-stroke

population is not known. Given the difficulty post-stroke of combining hip extension with knee flexion, necessary to take a backward step, we hypothesize this BWSpeed-fall incidence relationship exists post-stroke as well. Specific Aim 3 will test the hypothesis that BWSpeed at 2-months post-stroke is a significant predictor of fall incidence over the next year 1 year period.

**Backwards walking challenges postural stability in a controlled and safe environment with a dynamic task similar to the type known to induce falls.**

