## **5. Specific Aims:**

**Aim #1:** Test the hypothesis that 1-year fall incidence is decreased for participants randomized to BWTraining administered at 2-months post-stroke (versus usual care comparison group).

**Hypothesis #1a:** BWTraining at 2-months post-stroke reduces the number of falls over the next year.

**Hypothesis #1b:** BWTraining at 2-months post-stroke increases gait speed, improves balance and increases balance confidence over the next year.

**Aim #2:** Test the hypothesis that BWTraining at 2 months (immediate) vs. 1-year (delayed) post-stroke is more effective at improving BWSpeed.

**Hypothesis #2a:** BWSpeed improvement from 2- to 14-months post-stroke is greater when BWTraining is delivered at 2 months versus 1 year post-stroke.

**Hypothesis #2b:** Improvements in forward gait speed, Functional Gait Assessment and Activities-Balance Confidence Scale from 2- to 14-months post-stroke are greater when BWTraining is delivered at 2 months versus 1 year post-stroke.

**Aim #3:** This exploratory aim will test the hypothesis that BWSpeed at 2-months post-stroke is a significant predictor of fall incidence over the next year 1 year period, after adjusting for other covariates.

**Hypothesis #3:** BWSpeed at 2-months will be a significant predictor of fall incidence during the first year post-stroke, after adjusting for other covariates.

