**Participant Recruitment and Screening.** Priority for participation in this study will be given to volunteers who are Veterans. To optimize our capability to recruit Veterans we will conduct the study's assessments and intervention at two locations: 1) The Malcom Randall VA Medical Center in Gainesville FL, and 2) Brooks Rehabilitation in Jacksonville, FL. Utilizing these two recruitment sites will assure us of reaching our planned recruitment of 142. Individuals post-stroke will be recruited from: 1) VA BRRRC site: a. Database (IRB#457-1999) of the Malcom Randall VA BRRRC, a VA RR&D Center of Excellence. The database contains over 400 individuals with stroke who have been screened by a neurologist and interdisciplinary team to gather preliminary information about medical, motor and cognitive status. All individuals in the database have signed informed consent and agreed to be contacted for research participation. b. VA Informatics and Computing Infrastructure (VINCI) is an initiative to improve researchers' access to VA data and to facilitate the analysis of those data while ensuring Veterans' privacy and data security. c. Clinician referrals from Select Rehabilitation – potential participants will be provided an IRB-approved study flier and if interested will provide signed authorization to be contacted by study personnel. 2) Brooks site: a. Brooks Active Research Registry: Brooks Rehabilitation in Jacksonville, FL is

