2. 10 Meter Walk Test: Participants, wearing a gait belt and guarded by a licensed physical therapist, will traverse a total distance of 14 meters, two times at their self-selected walking pace. The time to traverse the middle 10 meters will be recorded with a stop watch.
3. Lower Extremity Fugl-Meyer Motor Assessment: The participant's ability to move their paretic lower limb will be assessed in the supine, sitting and standing position.
4. Range of Motion: Range of Motion of the hips, knees and ankles of both lower limbs will be assessed. This assessment will take place in the supine and sitting positions.
5. Three-Meter Backward Walk Test. The test consists of a 1 meter warm-up distance, a timed 3 meter distance, followed by an additional 1 meter to continue walking. Participants will walk this distance two times and the speed will be averaged.

Participants who meet eligibility criteria following the screening assessment will be invited to sign Part 2 Consent, the Intervention Informed Consent Form. Intervention Informed Consent allows for baseline testing and study participation.

Following baseline assessment (Assessment A) participants will be randomized to either the Immediate Group (initiate BWTraining within 1-week of Assessment A) or the Delayed Group (initiate BWTraining at 1-year post-stroke).

BWTraining Intervention. The intervention consists of 18-21 sessions, 3x/week for 6 weeks. BWTraining will occur both on a treadmill and overground. BW training will consist of 20–30 minutes of step training with a BWST system, manual assistance provided by trainers, with rest periods provided as warranted followed by 15 minutes of overground gait training. A 20–30 min period of actual stepping on the treadmill is the goal with rest periods as needed. Each training session may last up to 1 hour and 30 minutes including time for warm-up, stretching, and cool down. Participants will be fitted with a harness around their hips and torso, which will be attached to an overhead support system directly above the treadmill. From a stationary position, the treadmill belt will gradually be increased in speed with intervention trainers assisting participant to step backward with their paretic leg, their non-paretic leg (if needed) and at the hips for weight-shift.

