Three-Meter Backward Walk Test. We will use this test to collect our variable of interest, BWSpeed. The test consists of a 1 meter warm-up distance, a timed 3 meter distance, followed by an additional 1 meter to continue walking. Participants will walk this distance two times and the speed will be averaged.

Functional Gait Assessment (FGA). a 10-item clinical gait and balance test during which participants perform the following activities: walk at normal speeds, at fast and slow speeds, with vertical and horizontal head turns, with eyes closed, over obstacles, in tandem, backward and while ascending and descending stairs. Excellent test-retest and intra- and inter-rater reliability has been established patients post-stroke.

Activities-Specific Balance Confidence Scale (ABC): This 16-item self-report measure is used to assess perceived efficacy (self-reported confidence) in maintaining balance while performing a number of activities common in community-dwelling older adults.

Berg Balance Scale (BBS): This tool consists of 14 items that assesses static and dynamic standing balance, ability to sit, stand up and transfer. From our previous work characterizing and identifying risk factors for falls post-stroke, BBS scores  $\leq 42/56$  was the single best predictor of multiple/injurious falls. This assessment is ubiquitously used in stroke rehabilitation and will aide in describing our study cohort. This has been tested in a stroke population and has well-established reliability and validity.

Lower-Extremity Fugl-Meyer Motor Score: This tool consists of 17 items that assess motor control of the lower extremity as participants move their hip, knee and ankle in lying, sitting and standing is probably the most widely known scale of motor and sensory recovery after stroke. This assessment will provide a description of lower extremity impairment and aide in describing our study cohort.

Four-Step Square Test: This clinical test of dynamic standing balance examines the ability to step over small objects, change direction and includes taking a backwards step. In a

study that confirmed the feasibility and validity of this assessment for individuals post-stroke, those who reported a fall scored > 15 sec to complete the assessment.

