Data Analysis Plan: For Specific Aim #1 (primary outcome for entire study is the average fall rate per year), we will calculate the total number of falls per patient year for the Immediate intervention and Delayed intervention (control) groups, and use the actuarial method described below to estimate the average hazard rate in each group, and the overall hazard ratio. We will compare the Immediate and Delayed groups' fall rate at Assessment D, 1-year post-stroke. The analysis takes repeated falls within the same subject into account. Consider the number of falls,  $Y_{ij}$  for the  $j$ -th patient on treatment  $i$  ( $i=1,2$ ) in the year, and  $T_{ij}$ , the time at risk for the subject (usually 1 year, less for withdrawals before then). The estimated average fall hazard for treatment  $i$  is the ratio estimator  $H_i = \sum Y_{ij} / \sum T_{ij}$ . Under nonparametric considerations, if the true average hazard over subjects and time for treatment  $i$  is  $\Theta_i$ , then by the delta method,  $\text{Log}(H_i) - \text{log}(\Theta_i)$  ( $\text{Log}=\text{natural log}$ ) is asymptotically normal with mean zero and variance  $V_i$ ,  $i=1,2$  defined by

$$V_i = \{ \{ \text{Var}(Y_{ij}) / (\text{Mean } Y_{ij})^2 \} + \{ \text{Var}(T_{ij}) / (\text{Mean } T_{ij})^2 \} - 2 \text{Cov}(Y_{ij}, T_{ij}) / (\text{Mean } Y_{ij}) / (\text{Mean } T_{ij}) \} / N_i$$

with the means, variances, and covariance, the sample moments, and  $N_i$  is the sample size for treatment  $i$ . The log of the estimated average hazard ratio  $\text{Log}(H_2/H_1)$  is asymptotically normally distributed with mean  $\text{Log}(\Theta_2 / \Theta_1) = \text{Log}(\Theta_2) - \text{Log}(\Theta_1)$  and asymptotic variance  $(V_1 + V_2)$ . This enables us to obtain a two-sided P-value and after taking natural anti-logs, a point estimate and 95% confidence interval for the true average hazard ratio.

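### The Aim 1 fall-rate comparison ignores baseline Berg score and backward walking speed; prespecified adjustment is a cheap, modest and conditional gain in precision

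*Combined protocol and SAP*

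**What the plan says.** The Data Analysis Plan in section 6 says the primary analysis will "use the actuarial method described below to estimate the average hazard rate in each group, and the overall hazard ratio". Each arm's rate is its total falls divided by its total time at risk. The log ratio of the two rates is tested with a delta-method variance. No covariate or site appears, and the Abstract describes the same analysis.

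Berg score and the three-metre backward walk are done at the in-person screen and again in the assessment battery. Assessment A of that battery comes before allocation: "Following baseline assessment (Assessment A) participants will be randomized to either the Immediate Group". The study runs "assessments and intervention at two locations", and no stratification factor is stated.

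On prognosis, Hypothesis #3 is that "BWSpeed at 2-months will be a significant predictor of fall incidence during the first year post-stroke, after adjusting for other covariates". The Background adds: "Clinical tests of walking speed and postural balance to predict fall risk after stroke have been reported previously". Three passages limit this:

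- BWSpeed after stroke is still a conjecture ("we hypothesize this BWSpeed-fall incidence relationship exists post-stroke as well"), and Aim 3 is labelled exploratory.
- Under Outcome Measures, a Berg score of 42 or below "was the single best predictor of multiple/injurious falls". That cut is an entry criterion, so everyone enrolled is on the same side of it.
- The Abstract warns that "increased mobility may increase risk for falls", so the relation need not run in one direction.

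**The concern.** The plan expects baseline walking ability to predict falls in Aim 3, yet Aim 1, its only powered comparison, leaves that information in the error term. If Hypothesis #3 is right and the relation is roughly monotone, the Aim 1 confidence interval is wider than it needs to be, and data already in hand would narrow it.

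There is a second, smaller issue. With no stratification stated, a chance imbalance in a baseline score is possible. Any adjustment chosen after seeing it would be open to challenge.

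**Working it through.** **1. The plan's own figure.** Inputs from the Power analysis: 1.8 against 1.2 falls per year, Poisson, two-sided 0.05, 80% power, one year.

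- Log rate ratio with pooled null variance: n per arm = [1.960·√(2/1.5) + 0.842·√(1/1.8 + 1/1.2)]² / (ln 1.5)² = 64.4, against 64 stated.
- Power at 64 per arm with unpooled variance: SE = √[(1/1.8 + 1/1.2)/64] = 0.1473, and 0.4055/0.1473 − 1.960 = 0.792, which gives 78.6%.
- Simulating the plan's own test gives 78.7%. Adding the covariates gives 78.1%. Under the plan's Poisson assumption there is nothing to gain.

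**2. Is extra-Poisson variation plausible?** The Abstract reports 40 to 70% fallers in the first year. The Power analysis uses means of 1.5 and 1.8 falls per year.

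- Poisson would give 1 − e^(−1.5) = 77.7% and 1 − e^(−1.8) = 83.5% fallers.
- With gamma-distributed rates of squared coefficient of variation k, the non-faller share is (1 + kμ)^(−1/k). For μ = 1.5 and 30% non-fallers, k is about 0.35 (1.525^(−2.857) = 0.30). For μ = 1.8 it is about 0.63. Lower faller percentages need larger k.

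These figures come from different populations, so this is indicative only.

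**3. Variance with and without adjustment.** Let R be the share of k explained by the two scores; k and R are assumptions. There are 142/2 = 71 per arm. Entry at 2 to 4 months and an endpoint at 1 year give 8 to 10 months at risk, on average 0.75 years.

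- Crude variance: [(1/1.8 + 1/1.2)/0.75 + 2k]/71 = (1.852 + 2k)/71.
- Adjusted (Poisson likelihood, robust variance): about 1.024 × [1.852 + 2k(1 − R)]/71. The factor 1.024 is the simulated cost of three extra terms (2.3 to 2.5%).

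Example, k = 1 and R = 0.3: 1.024 × 3.252/3.852 = 0.864, a reduction of about 13.6%.

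**4. Simulated power.** 60,000 trials per cell under the alternative and 60,000 under the null. Adjusted is a log-link model with arm, both scores and site, using the HC1 sandwich. Matched change sets both tests to exactly 5% type I error.

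| k | R | Crude % | Adjusted % | Change | Matched change |
|---|---|---|---|---|---|
| 0.5 | 0 | 53.6 | 52.7 | −0.9 | −1.0 |
| 0.5 | 0.05 | 53.2 | 53.3 | +0.1 | −0.2 |
| 0.5 | 0.1 | 53.1 | 53.9 | +0.8 | +0.7 |
| 0.5 | 0.2 | 53.2 | 55.6 | +2.4 | +2.0 |
| 0.5 | 0.3 | 53.1 | 57.0 | +3.9 | +3.4 |
| 1 | 0 | 42.2 | 41.5 | −0.7 | −0.5 |
| 1 | 0.05 | 42.3 | 42.7 | +0.4 | +0.2 |
| 1 | 0.1 | 42.0 | 43.4 | +1.4 | +1.3 |
| 1 | 0.2 | 42.6 | 46.3 | +3.7 | +2.9 |
| 1 | 0.3 | 42.6 | 48.4 | +5.8 | +4.8 |

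Only the differences belong to this point. The low power levels come from the assumed k and the 8 to 10 months at risk.

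- For R = 0.1 to 0.3 the simulated variance falls by 1.5 to 13.7%. As participants, 142 × (1/variance ratio − 1) is about 2 to 23. At R = 0 about 3 are lost.
- Break-even is R of about 0.05, a fall-rate ratio per SD of the combined score of exp√ln(1 + Rk) = 1.17 (k = 0.5) to 1.25 (k = 1).
- The geometric mean rate ratio is 0.66 to 0.67 for both methods, so the target does not move.

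**5. Less favourable covariates** (HC1, R = 0.1 to 0.3; the shapes are assumptions).

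- Berg truncated at 42 and 13.5% at speed 0: +0.7 to +5.8 points.
- The same with reliability 0.8: +0.6 to +4.2.
- Threshold effect fitted by straight lines: +0.5 to +3.4.
- U-shape: −0.7 to −1.0.

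**6. Participants who cannot complete the backward walk.** Entry requires walking only 10 feet with one-person assistance, while the test covers 5 metres in all. Assume 13.6% cannot complete it and R = 0.2. Coding them as speed 0 gives 55.4% against 53.2% crude (k = 0.5) and 46.4% against 42.8% (k = 1). Dropping them gives 47.4% and 39.8%, worse than crude by 5.8 and 3.0 points.

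**7. Chance imbalance.** The SD of the difference in means is √(2/71) = 0.168 SD, so a gap above 0.25 SD has probability about 14%. Such a gap in the combined score shifts the crude rate ratio by a factor exp(0.25·√ln(1 + Rk)), or 6 to 14% for Rk from 0.05 to 0.3.

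**The case against.** The strongest reply is that nothing is wrong. The ratio estimator is fully specified and valid for any distribution of falls within patients, which the Power analysis gives as its merit. On the plan's own Poisson assumption, adjustment loses slightly. That part stands: this is an optional gain in efficiency. It is weakened by the plan's own faller percentages, which fit poorly with Poisson at the planned means.

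The value of R is also undocumented, and restricted entry may lower it. If Berg were normal(38, 10) before truncation to 8 to 42, its variance in the cohort would be about 45% of the untruncated value. A Berg-only R of 0.1, 0.2 or 0.3 would then shrink to about 0.05, 0.10 or 0.16. This stands, and it makes the top of the range optimistic for Berg. It does not apply directly to BWSpeed, which is not an entry criterion. The truncated-Berg runs above do not answer it, because they assume R of 0.1 to 0.3 within the enrolled cohort.

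Part of the HC1 gain is test size: type I error is 5.3 to 5.9%, against 5.2 to 5.7% crude. The matched column removes this. HC3 holds 4.8 to 5.1%, but power then changes by only −1.0 to +2.8 points for R = 0.1 to 0.3, and by about −2.3 at R = 0. At matched size HC1 and HC3 agree within 0.2 points.

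Finally, adjustment brings a new way to lose power, through dropped non-completers. That is true, so the coding rule has to be part of the change.

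**Conclusion.** The concern holds as a point about efficiency. The Aim 1 analysis is unadjusted although two plausible predictors are measured on everyone before randomisation. For k of 0.5 to 1 and R of 0.1 to 0.3, prespecified adjustment is worth about 0.7 to 4.8 power points at matched size (0.8 to 5.8 with HC1 as it stands). If the scores are not prognostic, are related to falls in a U-shape, or falls are purely Poisson, it costs about 1 point. In no overdispersed case in the table does it bring power back to 80%.

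The size rests on k and R, which the documents do not give, and confidence in it is medium. The case for the change is that the loss is small and bounded, the possible gain is larger, and the cost is wording. It also settles in advance how a chance baseline imbalance will be handled.

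**What to change.** Before any fall data are compared by arm, prespecify the Aim 1 primary analysis as follows:

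- A Poisson-likelihood, log-link model of each participant's fall count with offset log(time at risk), and terms for arm, continuous Berg score, continuous BWSpeed and site.
- The HC1 sandwich variance, named as the only one, with the rate ratio and its 95% confidence interval reported.
- Assessment A values as the covariates, with the screening value where Assessment A is missing.
- Every randomised participant kept in the model, with those unable to complete the backward walk coded as speed 0.
- The planned crude ratio estimator reported alongside as a sensitivity analysis.

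The cost is analysis-plan text only: no new data, visits or participants, and the rate ratio remains the target. The downside is a 2 to 3% rise in variance, or about 1 power point, if the scores predict nothing or only in a U-shape. If the rule for non-completers is left out and they are dropped, the loss against the crude analysis is about 3 to 6 points.
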